## 5 STATISTICAL METHODS

There are two primary endpoints hypothesis for this study and 10 types of descriptive endpoints. Both primary endpoints must be met for trial success.

### 5.1 Primary Safety Endpoint

The primary safety endpoint is the rate of device- or procedure-related serious adverse events occurring within 7 days of the index procedure. The CEC will make the final determination whether or not an adverse event meets the criteria for the primary endpoint.

#### 5.1.1 Hypothesis

The hypothesis is formally expressed as:

$H_0: P \geq 16.2\%$

$H_a: P < 16.2\%$ ,

where P is the percentage of subjects with a primary safety endpoint event. The hypothesis will be tested based on a one-sided exact test of binomial proportions at the one-sided 0.05 alpha level. The performance

goal of 16.2% is based on relevant experience from prior clinical trials using the TactiCath family of ablation catheters.

### 5.1.2 Analysis Methodology

The primary safety endpoint event rate will be calculated based on the number of subjects experiencing a primary safety endpoint divided by the total number of subjects in the analysis population. The null hypothesis will be rejected if the upper bound of the one-sided 95% exact binomial confidence interval for the proportion of subjects with the primary safety endpoint is less than 0.162. Subjects who terminate the study prematurely without experiencing any primary safety endpoint events will be excluded.

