- Consistent with data published in the 2017 HRS/EHRA/ECAS/APHRS/SOLAECE Expert Consensus Statement on Catheter and Surgical Ablation for Atrial Fibrillation, the following standard of care peri-procedure precautions are strongly recommended to minimize risks to subject safety:
  - Esophageal temperature monitoring – it is strongly recommended that esophageal temperature be monitored using an esophageal temperature probe at the anatomical location nearest the site of energy delivery. An alternative is esophageal deviation.
  - Termination of energy is strongly recommended if a >1°C rise in esophageal temperature is observed.

- Intracardiac echocardiography (ICE) – use of a phased-array ICE probe during the procedure to guide septal puncture and to monitor catheter position and manipulation is strongly recommended.
- Use of robotic systems to assist in the procedure is not allowed.
- Please refer to the catheter's IFU for further details.
- PVI must be documented and verified via entrance block with a multipolar catheter at or beyond 30 minutes from the last ablation lesion for each vein.
- Use of adenosine and / or isoproterenol is acceptable to assist in finding gaps.
- Cardioversion is allowed after PVI to assist with checking for isolation.
- The data from the entire procedure recorded on the commercial EnSite system should be anonymized and backed up on a USB drive and sent to the sponsor within reasonable timelines.
- It is strongly recommended that the operator personally evaluates the subject on the evening of the procedure as well as on the following morning, and maintains active surveillance of the subject's postoperative care and condition.

If for any reason the subject has the TactiCath SE inserted into their vasculature, but no ablation is performed, the subject will be followed up for 30 days to assess safety, then exit the trial.

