### 5.6 Subject Study Completion

Subject participation in the clinical investigation will conclude upon completion of the 12-Month visit. Upon completion of subject participation in the clinical investigation, the subject will return to standard of care.

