#### 6.1.1.1 Analysis Methodology

The primary safety endpoint event rate will be calculated based on the number of subjects experiencing a primary safety endpoint divided by the total number of subjects in the analysis population. Relatedness of the event to the catheter and to the procedure will be determined by the CEC. The null hypothesis will be rejected if the upper bound of the one-sided 95% confidence interval for the proportion of subjects with a primary safety endpoint is less than 16.2%. Subjects without an event that are lost to follow up without a visit at or beyond their 30-day follow up visit window will be excluded from this analysis.

[REDACTED]

[REDACTED]

[REDACTED]

[REDACTED]

[REDACTED]

[REDACTED]

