## Statistical Analysis Plan

- AV block
- Cardiac Perforation/Tamponade
- Death
- Diaphragmatic paralysis
- Gastroparesis
- Hospitalization
- Myocardial Infarction
- Pericarditis
- Pneumothorax
- Pulmonary edema
- Pulmonary vein stenosis
- Stroke
- Thromboembolism
- Transient ischemic attack
- Vascular access complication

These events must meet the criteria listed in Appendix C of the CIP to be included in the primary endpoint and will be adjudicated by an independent clinical events committee (CEC). Atrial-esophageal fistula, cardiac perforation/tamponade, and pulmonary vein stenosis that occur >7 days post procedure through 30 days will also contribute to the primary endpoint.

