### 5.1.4 Analysis Population

The analysis population for this endpoint will include all enrolled subjects who have also had the TactiCath SE inserted into their vasculature, and either had an event or completed a visit at or beyond their 30-day follow up visit window. Subjects without an event that are lost to follow up without a visit at or beyond their 30-day follow up visit window will be excluded from this analysis.

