### **5.1.6 Sensitivity Analysis**

To demonstrate robustness with respect to missing data, a tipping point analysis will be performed for the primary safety endpoint. This will involve imputing all possible combinations of outcomes for the primary endpoint among subjects who terminate the study prematurely without experiencing any primary safety endpoint events.

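### SAP 5.1.2 drops event-free early leavers with no time limit, while SAP 5.1.4 and the Protocol keep those with a 30-day visit; SAP 5.1.6 needs the same correction

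*SAP*

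**What the plan says.** **SAP 5.1.2** computes the safety rate as subjects with an event "divided by the total number of subjects in the analysis population", then adds: "Subjects who terminate the study prematurely without experiencing any primary safety endpoint events will be excluded". The SAP does not define premature termination.

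**SAP 5.1.4** defines the analysis population as subjects with the catheter inserted who "either had an event or completed a visit at or beyond their 30-day follow up visit window". Protocol 6.1.1.3 has the same definition.

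**Protocol 6.1.1.1**, the counterpart of SAP 5.1.2, carries a time limit in the same position: event-free subjects "lost to follow up without a visit at or beyond their 30-day follow up visit window will be excluded from this analysis".

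**Timing.** The endpoint covers 7 days. In addition, atrial-esophageal fistula, cardiac perforation or tamponade, and "pulmonary vein stenosis that occur >7 days post procedure through 30 days will also contribute to the primary endpoint" (SAP 4.1). Participation lasts much longer: "Subject participation in the clinical investigation will conclude upon completion of the 12-Month visit" (Protocol 5.6).

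**SAP 5.1.6** states its purpose: "To demonstrate robustness with respect to missing data, a tipping point analysis will be performed for the primary safety endpoint". It then defines the subjects to be imputed as event-free early terminators, again with no time limit and no requirement that the catheter was inserted.

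**The concern.** A subject's safety outcome is complete once the 30-day period has been observed. Leaving at month 5 does not make it missing. The last sentence of SAP 5.1.2, taken as written, nonetheless removes that subject from the denominator of a co-primary pass/fail test, while SAP 5.1.4 keeps the same subject. The plan thus holds two written denominators, and nothing in the SAP says which takes precedence. That choice should be closed before the data are seen.

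SAP 5.1.6 carries the same defect into the sensitivity analysis. An exercise meant for missing data would assign hypothetical events to subjects already known to be event-free, and so could look more fragile than the data warrant.

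**Working it through.** **No plan figure to reproduce.** The sample-size sections are redacted, and the readable text gives no assumed event rate, power or attrition. The check therefore uses the decision rule itself.

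**Inputs from the documents.** One-sided alpha 0.05, exact binomial (SAP 5.1.1); pass if the exact one-sided 95% upper bound is below 0.162 (SAP 5.1.2); at least 140 subjects at the report and 156 enrolled (SAP 3).

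**Formula.** For x events in n subjects, U(x, n) is the 95th percentile of a Beta(x + 1, n − x) distribution (Clopper-Pearson). Pass if U < 0.162.

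**Step 1: largest passing count.** It is 14 for n = 132–138, 15 for n = 139–145, 16 for n = 146–152 and 17 for n = 153–156.

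**Step 2: hold events fixed and remove event-free subjects.**

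| Events | n | Upper bound | Result |
|---|---|---|---|
| 15 | 140 | 16.02% | pass |
| 15 | 139 | 16.13% | pass |
| 15 | 138 | 16.24% | fail |
| 17 | 156 | 15.90% | pass |
| 17 | 152 | 16.30% | fail |

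Removing event-free subjects can only raise U. Any result that passes under the literal SAP 5.1.2 rule therefore also passes under SAP 5.1.4; the reverse need not hold.

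**Step 3: exclusions needed to turn a pass into a fail,** for every n from 140 to 156:

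- at the largest passing count, 1 to 7 (2 at n = 140, 7 at n = 145, 1 at n = 146 and n = 153, 4 at n = 156);
- one event below it, 8 to 14;
- two events below it, 15 to 22.

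**Step 4: chance that the two rules give different verdicts.** With k event-free leavers who have a 30-day visit, the verdicts differ when c(n − k) < X ≤ c(n), where c is the largest passing count and X is binomial (n, p). The documents give neither k nor p, so both are assumptions.

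| k | n | p = 6% | p = 8% | p = 10% |
|---|---|---|---|---|
| 1 | 140 or 156 | 0% | 0% | 0% |
| 1 | 146 | 0.8% | 4.8% | 9.8% |
| 1 | 153 | 0.6% | 4.1% | 9.2% |
| 4 | 140 | 1.1% | 5.7% | 10.4% |
| 4 | 145 or 150 | 0% | 0% | 0% |
| 4 | 156 | 0.7% | 4.6% | 9.5% |

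The chance depends on where the final n falls relative to the steps in c(n). In each non-zero row, c drops by one, so the entry is the probability of exactly c(n) events.

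**Step 5: the tipping-point set.** As an illustration, assume 11 events in 140 and five known-clean subjects in the set. The bound then runs from 12.67% (11/140) to 16.84% (16/140). Only the corner with all five turned into events fails, since 15/140 still passes. With the set limited to subjects whose outcome is really unknown, and none such present, it stays at 12.67%. If the illustration starts from 10 events, the worst case is 15/140 and no corner fails.

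**The case against.** The strongest reply is that an ordinary reading already settles the denominator. SAP 5.1.2 divides by the analysis population, SAP 5.1.4 is the section that defines it, and two Protocol sections agree. SAP 5.1.6 ties the same phrase to missing data, which suggests that the authors meant leaving before the endpoint could be assessed. Much of this stands: SAP 5.1.4 is the likely intention. But the sentence in SAP 5.1.2 is a separate exclusion, it lacks the limit that its Protocol counterpart has, and no precedence is stated.

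The documents do not support four stronger readings that a reader might infer.

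- **That the wording favours the device.** It does the opposite, because it removes only subjects without events.
- **That a whole group is dropped by design.** For a subject with the catheter inserted but no ablation, Protocol 5.3.2 says "the subject will be followed up for 30 days to assess safety, then exit the trial". Completing a planned exit is not naturally premature termination, and SAP 5.1.4 keeps those with the visit. The example is arguable, and no number is given for the group.
- **That SAP 5.1.6 could fail the trial.** It is not a success criterion under SAP 5.7, and the failing corner above depends on chosen values.
- **That the 140-subject trigger is part of the same error.** Protocol 4.1 and SAP 3 count subjects lost to follow-up toward 140, while Protocol 6.5 and SAP 5.6 require 140 with data available. This concerns when the report is made, not who is analysed. Text beside the trigger sentences is redacted, and they say at least 140, so a shortfall in the analysed number cannot be inferred.

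**Conclusion.** The point holds as a minor error in a stated rule. The last sentence of SAP 5.1.2 contradicts SAP 5.1.4 and Protocol 6.1.1.1 and 6.1.1.3, and SAP 5.1.6 repeats the open-ended wording. Confidence in the textual conflict is high.

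The consequence is limited. The literal rule cannot produce a false pass, and it can cost a true one only when the event count sits close to the limit. Under the assumptions in Step 4, the chance of a different verdict is between 0% and about 10%. These figures rest on assumed numbers of leavers and assumed true rates, and serve only to show the range.

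The mismatch between the two statements of the 140-subject trigger is a separate matter, held with lower confidence because of the redactions.

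**What to change.** - **SAP 5.1.2:** delete the last sentence, so that the SAP 5.1.4 population governs. Copying the Protocol 6.1.1.1 sentence instead would be less sound. It speaks only of subjects lost to follow-up, a status that Protocol 5.7 defines separately, so an event-free subject who withdraws at day 10 would not be covered by it. The inclusion rule in SAP 5.1.4 already handles that case.
- **SAP 5.1.6:** restrict the imputation set to catheter-inserted, event-free subjects without a visit at or beyond the 30-day window, whether lost or withdrawn.
- **Separately:** reconcile Protocol 4.1 and SAP 3 with Protocol 6.5 and SAP 5.6, stating whether lost subjects count toward 140.

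The cost is wording only: no extra subjects, visits or delay. The changes should be made before the primary analysis.

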### 5.1.3 Sample Size

[REDACTED]

### 5.1.4 Analysis Population

The analysis population for this endpoint will include all enrolled subjects who have also had the TactiCath SE inserted into their vasculature, and either had an event or completed a visit at or beyond their 30-day follow up visit window. Subjects without an event that are lost to follow up without a visit at or beyond their 30-day follow up visit window will be excluded from this analysis.

### 5.1.5 Poolability Analysis

#### 5.1.5.1 Multiple Geography Effect

The trial will be conducted in 35 sites in the United States, Europe and Australia following the same investigational plan and inclusion and exclusion criteria. The trial will be conducted following the same procedures, monitoring plan and training plan in all regions. Poolability of the primary safety endpoint across region (i.e., US vs. OUS) will be evaluated for subjects included in the primary analysis population.

To evaluate the geography effect on the primary safety endpoint, Fisher's exact test will be tested for geography effect in the TactiSense trial against an alpha level of 0.15. If the p-value is less than 0.15, Abbott will examine subject demographics, baseline clinical characteristics for possible correlations and confounding factors.

#### 5.1.5.2 Multiple Center Effect

Analysis will be performed by pooling data across study sites. The TactiSense trial will have 35 sites globally, with at least 50% of subjects in the United States. Subject enrollment is capped at 28 per site (20% of the total number of enrollments). This cap per site will prevent the scenario where the results from a few sites dominate the overall study result. For the analysis of center effect, data from smaller sites may be combined for the analysis. Smaller sites are defined as sites with fewer than 12 subjects per site. The pooling of the smaller sites will be based on the following rules:

[REDACTED]

- Sort all smaller sites based on the number of subjects per site in an ascending order. If there are ties, sort further by site number.
- Starting from the smallest site in this list, combine sites by going up the list until the combined group size first reaches 12 or larger. At this point, a super site is identified.
- Repeat the above grouping process from the next smallest site above the newly formed super site.
- The grouping process ends when all smaller sites have been accounted for.

The sizes of the super sites (which are a result of grouping smaller sites) will range between 12 and up to 22 (11+11). This represents a reasonable range of sample sizes which will provide meaningful estimates of within-sites variations and will not alter between-sites variation.

To evaluate the multiple center effect on the primary safety endpoint, Fisher's exact test will be tested for center effect in the TactiSense trial against an alpha level of 0.15.

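### Does the center-effect test in SAP 5.1.5.2 need a stated follow-up, fixed groups and a site-adjusted safety bound?

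*SAP*

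**What the plan says.** The primary safety decision is in SAP 5.1.2: "The null hypothesis will be rejected if the upper bound of the one-sided 95% exact binomial confidence interval" lies below 0.162. Section 5.6 puts the primary analysis at 140 subjects with data. Section 5.7 makes trial success depend only on rejecting the two primary null hypotheses.

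Site is handled in 5.1.5.2. The main analysis is simple: "Analysis will be performed by pooling data across study sites". For the center check, sites with fewer than 12 subjects are small, and "data from smaller sites may be combined for the analysis". The rule sorts them by size, breaks ties by site number and closes a group once it reaches 12. It ends: "The grouping process ends when all smaller sites have been accounted for". The stated size range of the combined groups is 12 to 22. A redaction mark stands between the lead-in to the rules and the rules themselves. On the cap of 28 the section says: "This cap per site will prevent the scenario where the results from a few sites dominate the overall study result". It closes with the test: "Fisher's exact test will be tested for center effect in the TactiSense trial against an alpha level of 0.15".

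For geography, 5.1.5.1 uses the same test and level and adds: "If the p-value is less than 0.15, Abbott will examine subject demographics, baseline clinical characteristics for possible correlations and confounding factors". The only visible sensitivity analysis for safety is in 5.1.6: "To demonstrate robustness with respect to missing data, a tipping point analysis will be performed for the primary safety endpoint". Section 6 of the protocol refers poolability to the SAP and adds nothing on it.

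**The concern.** Four things look wrong together.

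- The center test has no stated consequence although its geography twin has one, so the response to a small p-value would be chosen after seeing the data.
- The tested groups seem open: combining is worded as optional, and the visible rule has no place for a last group below 12.
- The exact binomial bound treats the pooled subjects as independent, and no visible analysis shows the bound with site differences allowed for.
- The reassurances are too strong. Three sites at the cap would hold 84 of 140 subjects (60%), SAP 3 lets the sponsor waive the 20% limit, and merging sites does in general change between-site variation.

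The pooled bound is the safety claim for the marketing application. If site clustering raised the chance of passing at a true rate of 16.2% well above 5%, the claim would be weaker than it looks.

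**Working it through.** **Inputs.** From the SAP: 16.2% goal and one-sided 0.05 (5.1.1, 5.1.2); 140 subjects (5.6); 35 sites, threshold 12, cap 28, level 0.15 (5.1.5.2); 156 enrollments at up to 35 sites (section 3). Assumed, because the documents do not give them: site sizes and the ICC of the safety event.

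**1. The plan's own figures.**
- Cap: 0.20 × 140 = 28, but 0.20 × 156 = 31.2. The 28 reproduces only on the base of 140.
- Size range: a group still open holds at most 11 and the next small site adds at most 11, so a completed group holds 12 to 22. That reproduces.
- Leftover: with 35 sites of 4, three sites make 12. Since 35 = 11 × 3 + 2, there are 11 groups of 12 and a leftover of 2 × 4 = 8, outside the stated range. About half of 19,907 random layouts left such a remainder.

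**2. The pooled test.** The largest c with P(X ≤ c; 140, 0.162) ≤ 0.05 is 15. The upper bound is 16.02% at 15 events and 16.84% at 16. The error at 16.2% is 4.45%.

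**3. Sites taken as they are.** If site i has n_i subjects and its own rate p_i, the pooled count has variance n·p̄(1 − p̄) − Σ n_i(p_i − p̄)², which never exceeds the binomial variance. The pass limit of 15 lies well below the expected 140 × 0.162 = 22.68 events. There the lower tail is at most the binomial one (Hoeffding's inequality for unequal Bernoulli trials), so the error stays at or below 4.45%.

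**4. Sites taken as a random sample of centers.** Beta-binomial simulation with mean 16.2%, giving P(X ≤ 15):

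| Layout (140 subjects) | ICC 0.01 | 0.02 | 0.05 | 0.10 |
|---|---|---|---|---|
| 35 sites of 4 | 4.6% | 5.0% | 5.7% | 6.8% |
| 35 skewed sites | 5.1% | 5.0% | 6.2% | 8.0% |
| 20 skewed sites | 5.2% | 6.1% | 8.1% | 11.3% |
| 3 of 28 plus 14 of 4 | 5.7% | 7.1% | 10.7% | 15.9% |
| 5 of 28 | 6.6% | 8.5% | 13.8% | 20.2% |

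The first row follows from the design effect: 1 + (4 − 1) × 0.05 = 1.15. The last two rows use 17 and 5 sites, against the 35 in 5.1.5.2.

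**5. Does the choice of groups matter?** For 35 sites of 4 at a 16.2% rate, the chance of p < 0.15 is 24% at ICC 0.05 and 34% at ICC 0.10, whether the leftover of 8 is kept or merged. In single data sets (10% event rate) that choice switches the verdict in 6% to 12% of those with a leftover, of which about 1 point is simulation noise. Not merging small sites at all switches it in 15% to 36%. In neither case does the primary result move, because the center test does not feed into it.

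**6. Would a site-clustered bound help?** Tested version: cluster-robust logit interval, t with sites minus 1 degrees of freedom, variance not below binomial.
- At 16.2% and ICC 0.05 it passes in 3.4% to 5.1% across the five layouts.
- At ICC 0.10 it passes in about 7.8% with three sites at the cap and 5.9% with 20 skewed sites.
- With no site effect it passes in only about 2.1% (three at the cap) and 0.8% (five sites).
- At a true 8% with no site effect, the exact test passes in about 91%. The clustered bound also passes in 88% (35 sites), 86% (20 skewed), 82% (three at the cap) and 63% (five sites).

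**7. Leave-one-site-out.** At 15/140, dropping a 28-subject site with 0, 1 or 2 events gives bounds of 19.9%, 18.8% and 17.8%. But a site with exactly its share of events (28 × 15/140 = 3) leaves 12/112, the same rate, and the bound is still 16.8%. At a bare pass the bound therefore crosses 16.2% from lost sample size alone.

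**The case for a change.** The strongest case for a change is that it costs a few sentences and no data. The center test is prespecified, so its consequence should be too. The wording on combining is permissive whatever the redaction hides. The cap base and the reassurance about dominance do not survive arithmetic. Section 3 says up to 35 sites, so a concentrated layout is not excluded, and in one the random-site error could pass 10%. Among false passes at ICC 0.05, the center test gives p < 0.15 in only 22% to 43%, so it cannot stand in for an analysis of the bound.

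The textual points stand. They carry less than they seem to.

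- The obvious response to a center signal is the one written one subsection earlier for geography, plus a table of rates by site. An analyst would do this unprompted, and it could not alter the success rule.
- The passage that permits combining goes on to say which rules pooling will follow and what sizes result, so the natural reading is that the rules apply. The missing leftover rule may lie under the redaction.
- The center test is a poolability screen. The SAP does not ask it to catch false passes.
- The larger error rates need an ICC that nobody has stated, a layout unlike the planned one, and a target population of centers that the SAP does not adopt.

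**Conclusion.** No change to the plan follows. The missing follow-up and the leftover group are gaps that analysts would fill sensibly. The cap of 28 is a clerical slip of base (140 against 156). The statements about dominance and between-site variation are overworded but decide nothing.

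The pooled exact test is valid as specified: 4.45% at 16.2%, and no higher for the average over participating sites. Under a random-site reading with 35 sites of 4, the error is 4.6% to 5.7% for ICC 0.01 to 0.05 and 6.8% at 0.10. Larger figures need fewer or much more unequal sites. These values rest on assumed ICCs and site sizes, and a few very large sites would call for more caution in reading a bare pass. Even then, the clustered bound is unreliable in just those layouts (about 7.8% at ICC 0.10 and 2.1% at ICC 0 with three sites at the cap), and it would leave the primary test and the success rule as they are.
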